The trial will be conducted in accordance with International Conference on Harmonization Good Clinical Practice (ICH GCP), applicable United States (US) Code of Federal Regulations (CFR), and applicable VA policies, regulations and procedures. The Study Chairs will assure that no deviations from, or changes to the protocol will take place without prior agreement from the funding agency and documented approval from the VA Central Institutional Review Board (CIRB), except where necessary to eliminate an immediate hazard(s) to the trial participants. All personnel involved in the conduct of this study will have completed Human Subjects Protection and ICH GCP Training prior to participation in study activities.

The protocol, informed consent form, recruitment materials, and all participant materials will be submitted to the VA CIRB for review and approval. Approval of both the protocol and the consent form must be obtained before any participant is enrolled. Any amendment to the protocol will require review and approval by the VA CIRB before the changes are implemented to the study. All changes to the consent form will be VA CIRB approved; a determination will be made regarding whether a new consent needs to be obtained from participants who provided consent using a previously approved consent form.

EXECUTIVE SUMMARY

The very acute onset and rapid dissemination of SARS-CoV-2 (SARS-CoV-2) across the world over several months precluded the early availability of effective preventive and therapeutic interventions. The impact of SARS-CoV-2 is substantial with hospitalization of about 20% of those infected, half of whom require intensive care due to respiratory failure from which death may ensue. Prominent among those who preferentially experience this high incidence of morbidity and mortality are men over age 65 years with underlying comorbidities such as hypertension, diabetes, lung, heart, kidney or liver disease, obesity and immunocompromise^{1, 2}, clinical features commonly shared by the Veteran population. Effective therapies are currently quite limited. We propose to bolster immune defense against the virus with convalescent plasma that contributes antiviral antibodies and, potentially, non-antibody factors to its therapeutic activity.

Hospitalized Veterans with documented SARS-CoV-2 infection and evidence of early respiratory compromise (hypoxemia and requirement for oxygen) will be randomized to receive convalescent plasma or a masked saline placebo. The primary outcome is the rapidity and frequency of progression to respiratory failure or death in the two groups. The randomized, double-blind placebo-controlled design is essential to confirm the utility or the futility of convalescent plasma, building on mostly promising safety and outcomes with convalescent plasma in 6 anecdotal and case series of 56 patients with SARS-CoV-2³⁻⁸ and a small non-randomized trial with retrospective controls⁹. However, observational and non-randomized studies may miss systematic bias and are not always confirmed with controlled randomized trials for other viral infections^{10,11-15}, thus the rigorous controlled trial of convalescent plasma proposed in VA CoronavirUs Research and Efficacy Studies-1 (VA CURES-1).

1 PROTOCOL SUMMARY

1.1 SYNOPSIS

Title

VA CoronavirUs Research and Efficacy Studies-1 (VA CURES-1).

Study Description

The full VA CURES program is a newly initiated series of adaptive, double-blind placebo-controlled, randomized clinical trials (RCTs) to evaluate the safety and efficacy of novel therapeutic agents in hospitalized adults diagnosed with COVID-19. This framework will permit multicenter trials to be conducted in VA Medical Centers to compare different investigational therapeutic agents to a single contemporaneous control arm consisting of best supportive care (BSC). Interim monitoring will allow early stopping for futility, efficacy, or safety. After VA CURES-1 testing convalescent plasma vs saline is launched, new arms or new trials can be introduced according to scientific and public health needs. If one therapy proves to be efficacious, this treatment may become the control arm for comparison(s) with new experimental treatment(s). Any such change would be accompanied by an updated sample size and an amended protocol.

This adaptive platform is used to rapidly evaluate different therapeutics in a population of those hospitalized with moderate to severe COVID-19. The platform will provide a common framework sharing a similar population, design, endpoints, and safety oversight. New stages with new therapeutics can be introduced and will be described in a stage-specific appendix. One independent Data and Monitoring Committee (DMC) will actively monitor interim data in all stages to make recommendations about early study closure or changes to study arms.

This VA CURES adaptive design RCTs may involve multiple stages, each investigating different interventions. To convey clearly the protocol elements, interventions, objectives and endpoints for each stage, common elements are described in the main protocol document while each stage is noted in a stage-specific appendix.

The first stage in the clinical trial (VA CURES-1) is:

Stage 1: Convalescent Plasma vs Saline

If convalescent plasma is shown to be beneficial in Stage 1, we may proceed to the next stage (VA CURES-1a) under amended design and subsequent approval:

Stage 1a: Convalescent Plasma vs Fresh Frozen Plasma

If convalescent plasma is shown not to be beneficial in Stage 1, we will design a RCT testing an alternative agent.

Study Objectives

The primary objective of the VA CURES program is to evaluate the clinical efficacy of different investigational therapeutics compared with the control arm by binary analysis of the composite primary outcome of acute hypoxemic respiratory failure or all-cause death by Day 28. Acute hypoxemic respiratory failure is defined as the initiation of mechanical ventilation [either via

endotracheal intubation or as non-invasive positive pressure ventilation (NIPPV) for an indication other than for pre-diagnosed sleep apnea at outpatient settings] OR extracorporeal membrane oxygenation (ECMO).

The secondary objectives are to evaluate the clinical efficacy and safety of different investigational therapeutics compared to the control arm as assessed by the secondary efficacy outcomes and the safety outcomes defined in the stage-specific Objectives and Endpoints. Each stage may prioritize different secondary endpoints for the purpose of multiple comparison analyses.

Study Outcomes

Primary efficacy outcome: Proportion of participants developing acute hypoxic respiratory failure or all-cause death up to day 28.

Key secondary efficacy outcome: Time to recovery (as determined by attaining a score of 1,2 or 3 on the World Health Organization (WHO) 8-point ordinal scale).

Study Population

This trial will study putative therapeutics in a hospitalized adult population (≥ 18 years old) with moderate to severe COVID-19. The trial will have common inclusion and exclusion criteria but may be modified for each stage for the unique risk of the study product in that stage.

Inclusion Criteria

- 1) Age 18 or older.
- 2) Confirmed acute SARS-CoV-2 infection.
- 3) Requirement for supplemental oxygen therapy that is either new or at least 2 Lpm greater than previous outpatient chronic therapy.
- 4) Ability to provide written informed consent from patient or legally authorized representative (LAR).

Exclusion Criteria

- 1) anticipated hospitalization <48 hours.
- 2) anticipated respiratory failure (as defined above) or death within 48 hours.
- 3) Septic shock or multiple organ dysfunction or failure.
- 4) Current or anticipated participation in another randomized trial for SARS-CoV-2.

Study Phase

Phase 3

Study Sites

VA CURES-1 will initially engage 25 VA Medical Centers nationally. Site selection will be determined by presence of: 1) sufficient numbers of cases of COVID-19; 2) a committed local site investigator (LSI); 3) established infrastructure for clinical trials (study coordinator(s), research pharmacist, blood bank); 4) onsite clinical laboratory; and 5) laboratory facilities for study sample processing, labeling and storage. Multiple sites will be IRB-approved via VA CIRB, but site activation will be dependent on the incidence of SARS-CoV-2 at that site.

Study Intervention

Study interventions will vary depending on the stages or trials under VA CURES. VA CURES-1 compares convalescent plasma versus saline.

Study Duration

The series of studies comprising the full VA CURES adaptive study will last for up to 60 months. This specific protocol (VA CURES-1) will have a specific timeline (20 months) within the full VA CURES adaptive protocol. The study can be terminated early if the target number of participants is met or if the interim analysis demonstrates efficacy, harm or futility accordingly to protocol-specified stopping boundaries.

[figure not shown]
Participant Duration

An individual subject will complete the study in up to 35 days, from screening and randomization at Day -3 to 0, to follow-up on Day 29 + 3 days.

1.2 STUDY SCHEMA

This adaptive design clinical trial may involve multiple stages each investigating different interventions. In order to clearly convey the protocol elements, interventions, objectives and endpoints for each stage, common elements are described in the main protocol document while each stage is noted in a stage-specific appendix. Below is the study schema for Stage 1.

Figure 1. Study Schema

1.3 SCHEDULE OF ACTIVITIES (SOA)

Table 1. Schedule of Assessments

Day ± Window	Up to 72 hrs. prior to Randomization Time	Day 1	Up to 36 hrs. after Randomization Time	Day 2 - Hospital Discharge		Day 15 ±2	Day 22 ±3	Day 29 +3 ¹⁵
Procedures	Eligibility	Randomization/ Baseline	Product Administration	Hospitalization Period	Initial Discharge			Follow-up Visit 3 (29d)
Obtain signed Informed Consent ¹	X							
Obtain Demographics & Medical History data	X							
Perform physical exam	X							
Review -SARS-CoV-2 results	X							
Administer pregnancy test for females	X							
Review Eligibility	X							
Randomize participant		X ³						
Assess Admission Signs and Symptoms		X ⁴						
Collect Vital Signs ² (NEWS2)		X ⁴		X ⁹		X ¹³		X ¹³
Collect Clinical status data ²		X ⁴		X ⁹		X	X	X
Evaluate Adverse Events		X ⁴	X	X ⁹	X	X	X	X
Review Concomitant Medications		X ⁴	X ⁷		X	X	X	X
Obtain Safety Labs ⁵ -Hematology, chemistry, liver tests		X ⁴		X ^{10,12}		X ¹³		X ¹³
Obtain Exploratory Research Labs ⁶ -Blood -Respiratory sample		X ⁴		X ^{11,12}		X ¹³		X ¹³
Administer Study Product			X ⁸					
Obtain Discharge info					X			
Collect Readmission data, if applicable						X	X	X

Notes:

¹ This form is completed by the participant or legal representative.

² Refer to Section 8.1 of the protocol for details of clinical data to be collected including WHO ordinal score, National Early Warning Score (NEWS2), oxygen requirement, mechanical ventilator requirement, etc.

³ Randomization must occur within 72 hours of initial hospital admission.

⁴ Baseline assessments should be performed before the first study product administration:

- Day 1 safety labs and Day 1 exploratory research specimens can be collected up to 24 hours prior to randomization and before the first study product administration.
- Laboratory tests performed as part of routine clinical care up to 24 hours before randomization will be accepted for the baseline safety laboratory tests.
- See Visit Schedule Grid for more details.

⁵ Safety laboratory tests include WBC with differential, hemoglobin, platelets, creatinine, glucose, total bilirubin, alanine aminotransferase (ALT), aspartate aminotransferase (AST), and prothrombin time (PT).

⁶ Research Specimens include respiratory samples and 30mL of blood for research studies (2 tablespoons) as feasible. Nasopharyngeal (NP) swabs are preferred, but if these are not obtainable, oropharyngeal (OP), saliva (S) or anterior nares swabs (AN) may be substituted.

⁷ If product administration starts on day of randomization (Day 1), then concomitant medications only need to be reviewed one time, at day of randomization

⁸ Ideally, product administration should start on the same day as randomization (Day 1) but may be started up to 36 hours after randomization.

⁹ Obtain clinical status data, vital sign data (for NEWS2), and assess adverse events daily during hospitalization, both during initial hospitalization and for readmissions.

¹⁰ Obtain safety labs only on Days 2, 4, and 7 if hospitalized, including readmissions. Any laboratory tests performed as part of routine clinical care within the visit windows specified in Table 5 can be used for safety laboratory testing.

¹¹ Blood for research studies only on Days 2, 4, and 7 and swabs for RT-PCR only on Days 4, and 7, if hospitalized (includes readmissions).

¹² If not hospitalized at study site on Day 2, 4 or 7, no need to collect any labs or specimen on that day.

¹³ For Day 15, 22, and 29 follow-up visits:

- If not hospitalized and have an in-person visit on Day 15 and 29: collect NEWS2, safety laboratory tests, and research laboratory samples.
- If discharged, collect hospital readmission data at each subsequent visit.
- Day 22 visit (after discharge) is generally done by phone or telehealth.
- In-person visits (after discharge) are preferred and strongly encouraged for Days 15 and 29. However, when quarantine and other factors limit the participant's ability to return to the site for the visit, they may be performed by telehealth or by phone.

14 Hospitalization period includes initial hospitalization and readmissions.

15 The final visit cannot occur before Day 29.

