
4. To evaluate the safety of different investigational therapeutics as compared to the control arm as assessed by:
 
 • Cumulative incidence of SAEs through Day 29. • Cumulative incidence of Grade 3 and 4 clinical and/or laboratory AEs through Day 29. • Discontinuation or temporary suspension of study product administrations (for any reason) • Changes in complete blood count with differential, hemoglobin, platelets, creatinine, glucose, total bilirubin, alanine aminotransferase (ALT), aspartate aminotransferase (AST), and prothrombin time (PT) reported as international normalized ratio (INR) over time (analysis of lab values in addition to AEs noted above). 	
 • SAEs • Grade 3 and 4 AEs • Change in total WBC number, neutrophil number, lymphocyte number, hemoglobin, platelets, creatinine, glucose, total bilirubin, ALT, AST, and PT/INR from Day 1 to Days 2, 4, and 7 (while hospitalized); and Days 15 and 29 (if attends in-person visit or still hospitalized).
Exploratory	

1. To examine if the effect of convalescent plasma is associated with the days of symptoms at time of plasma administration
	
 • Plasma administered on day ≤ 7 vs. >7 days of symptoms on primary outcome

2. To examine if effect of convalescent plasma differs by comorbidities
	
 • Primary outcome in persons with ≤ 2 or ≥ 3 comorbidities (age ≥ 65 years, chronic lung, cardiac and renal disease, hypertension, diabetes, obesity and immunosuppression)

3. Research sample collection and management for future investigations:
 
Respiratory samples on days 1, 4, 7, 15, 29 and 30 mL of blood on days 1, 2, 4, 7 in hospital and days 15 and 29 in- or outpatient.
	
 • Sample Collection (Research lab draw with routine labs), preparation, labeling, shipping, storage and monitoring will be addressed in a future amendment.

4. Impact of donor convalescent plasma parameters on the activity of administered plasma
	
 • Donor plasma samples retained by Vitalant Blood services and provided to CURES-1 investigators will be tested for antibody levels, neutralization against SARS-CoV2, inflammatory and other mediators in relation to clinical and laboratory outcomes in study subjects.

World Health Organization (WHO) Ordinal Scale

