4.4 END OF STUDY DEFINITION

The study is completed for each subject on day 29 (+3 days) after administration of convalescent plasma or on the day of death.

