6.1.2 DOSING AND ADMINISTRATION

The dose of convalescent plasma, or placebo, that will be utilized in this study is consistent with the April 8, 2020 published by the FDA (<https://www.fda.gov/vaccines-blood-biologics/investigational-new-drug-ind-or-device-exemption-ide-process-cber/recommendations-investigational-covid-19-convalescent-plasma>). We will utilize a target dose of two units of plasma with antibodies to SARS-CoV-2, based on previously studied dosing established in SARS1, in which a weight-based dose of 5 mL/kg has been utilized.

Study intervention will be started within 36 hours of randomization, at a rate of 150 mL per hour or less. The administration of each unit should last approximately up to 2 hours, and the elapsed time between each transfusion should not exceed 12 hours. Time at start and end of transfusion should be recorded. Vital signs will be measured prior to transfusion, 10-20 minutes after start of transfusion, at completion of transfusion or if discontinued and 30-60 minutes after the end of the transfusion.

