6.5.1 CONCOMITANT MEDICATIONS

Use of concurrent medications is allowed if they are part of local best supportive care for SARS-CoV-2 infection.

Pretreatment with appropriate medication to minimize transfusion reactions (e.g. acetaminophen, diphenhydramine) may be given at the discretion of the local site investigator and consistent with local site's transfusion protocols.

Pre-admission level A medications will be collected by class at baseline. Concomitant medications taken for the prevention and treatment of COVID-19 in the 7 days prior to Study Day 1 (day of randomization) and concomitant medications prescribed from hospital admission through Day 28 will be collected by study site staff using the designated case report form. This information will be collected via chart review, or in person or telehealth/telephone interviews, when appropriate.

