8.3.1 MEASURES OF CLINICAL SUPPORT AND LIMITATIONS

On each study day through Day 29, the following measures for the previous day will be recorded. That is, on Day 3, Day 2 measures are assessed as occurring anytime in that 24 hours period (12 midnight to 12 midnight):

- Disposition (hospitalized -ICU, hospitalized – non-ICU, not hospitalized, died)
- Additional organ support (e.g., kidneys, blood pressure support)
- ECMO requirement
- Invasive mechanical ventilation (via endotracheal tube or tracheostomy tube) requirement
- Non-invasive mechanical ventilation requirement including CPAP (for an indication other than previously diagnosed sleep apnea)
- Heated high flow nasal cannula ≥ 15 L/min
- Supplemental oxygen requirement
- Limitations of physical activity (self-assessed)

Site staff will record the above measures daily during initial hospitalization. After discharge from initial hospitalization, site staff will collect the above measures via in-person (preferred), telehealth or telephone follow-up on Study Days 15 and 29, and via telehealth/telephone follow-up on Study Day 22. At the time of initial hospital discharge, participants will be provided with a log to help them record the above measures daily and report the data to site staff at follow-up.

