8.4.1 CLINICAL LABORATORY EVALUATIONS

- Blood will be drawn at the time points indicated in the *Schedule of Assessments (Table 1)* and in **Table 5**.
- Blood volumes are indicated in **Table 5**.
- Blood type will be determined on Day 1 before product administration.
- Fasting is not required before collection of laboratory samples.
- Minimal clinical safety laboratory tests include WBC, differential, Hgb, PLT, creatinine, glucose, total bilirubin, AST, ALT, and PT. Sites that do not have access to a test for PT/INR will be allowed to report an INR.
- Day 1 clinical laboratory evaluations are drawn prior to initial study product administration as a baseline and results do not need to be reviewed to determine if initial study product administration should be given.
- Clinical laboratory testing will be performed at each clinical trial site in real time.

Table 5: Blood volume and collection windows.

	Randomization/ Baseline					
Day +/- Window	1	2 + 1	4 + 1	7 ± 1	15 ± 2	29 ± 3
Safety hematology, chemistry and liver tests	X 14mL ¹	X ² 14mL ¹	X ² 14mL ¹	X ² 14mL ¹	X ³ 14mL ¹	X ³ 14mL ¹
Blood for research	X ^{4,5} 30mL	X ^{2,5} 30mL	X ^{2,5} 30mL	X ^{2,5} 30mL	X ^{3,5} 30mL	X ^{3,5} 30mL
Total blood volume	44mL	44mL	44mL	44mL	44mL	44mL
Total all study days	Up to 264 mL					

1. For Randomization/Baseline visit, total volume calculated assumes there are no laboratory tests done as part of routine clinical care up to 24 hours prior to randomization. For all other visits, total volume calculated assumes there were no laboratory tests performed as part of routine clinical care in the specified visit window for that assessment: Day 2 + 1, Day 4 + 1, Day 7 ± 1, Day 15 ± 2 and Day 29 ± 3, if still hospitalized (this includes initial hospitalization or re-hospitalization to the same VA hospital).

2. Safety laboratory tests and blood for research will be collected on Days 2, 4, and 7 if the participant is hospitalized at these time points (initial hospitalization or re-hospitalization at the study site).

3. Safety laboratory tests and blood for research will be collected on Day 15 and 29 if the participant is still hospitalized at these time points or if they return for an in-person outpatient visit and the site has the capacity to collect blood in the outpatient setting.

4. Collected before participant receives study product.

5. 30 mL (approximately 2 tablespoons) of blood will be collected.

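### The Day 2 safety labs and research blood are timed from randomisation with no rule placing them after the infusion, so some can be drawn before or during dosing

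*Combined protocol and SAP*

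**What the plan says.** **Clock.** Section 6.5.1 defines "Study Day 1 (day of randomization"). Section 8.3.1 treats a study day as "12 midnight to 12 midnight" for clinical status.

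**Dosing.** Table 1 note 8 (section 1.3) and section 8.2 prefer a start on the day of randomisation, but product "may be started up to 36 hours after randomization". Section 6.1.2 has each unit lasting up to about 2 hours, and "the elapsed time between each transfusion should not exceed 12 hours". It also requires infusion start and end times to be recorded.

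**Sampling.** Table 1 note 10: "Obtain safety labs only on Days 2, 4, and 7 if hospitalized, including readmissions". Note 11 sets the same days for research blood. Table 5 note 2 (section 8.4.1) repeats this: "Safety laboratory tests and blood for research will be collected on Days 2, 4, and 7 if the participant is hospitalized at these time points". Table 5 gives the first post-baseline sample a Day 2 +1 window, and Table 1 note 10 accepts routine-care safety labs within the Table 5 windows. Only the baseline sample has an order rule relative to dosing: it must precede product.

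**Use.** Table 2 (section 3) lists, under the safety objective, laboratory change "from Day 1 to Days 2, 4, and 7 (while hospitalized"). The safety population in Populations for Analyses is everyone who received at least one dose.

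**The concern.** The safety population is defined by having been dosed, yet its first post-baseline laboratory value need not follow any dose. A site that keeps exactly to the schedule can return a Day 2 value from before the first unit or from between the two units. Table 2 then pools it with genuine post-infusion values.

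Two things are at stake. One is the Day 1 to Day 2 laboratory change, a listed safety endpoint. The other is the first research-blood point after baseline, which supports the antibody work in section 8.3.5 and the planned paper on antibody response over time. A pre-infusion sample contains no transferred antibody and no product effect, so counting it as Day 2 pulls both toward no difference.

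A delayed start is plausible. Section 6.2.1 allows plasma to be shipped overnight to the requesting centre, and section 8.4.1 has blood type determined on Day 1 before administration.

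**Working it through.** The plan gives no figure for this, so there is none to reproduce. The check is timeline arithmetic, then an illustration under stated assumptions.

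**1. Timeline.** Let *t* be the clock hour of randomisation on Day 1, in hours from 00:00. Inputs: latest start 36 h (Table 1 note 8), unit duration about 2 h and maximum gap 12 h (6.1.2), window Day 2 +1, or hours 24 to 72 (Table 5). The midnight-to-midnight day is assumed to apply to labs as well.

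- Latest start = *t* + 36.
- Latest end = *t* + 36 + 2 + 12 + 2 = *t* + 52, or *t* + 36 + 12 + 2 = *t* + 50 if the gap is counted start to start.

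| Randomised (Day 1) | Latest start | Latest end (52 h) |
|---|---|---|
| 00:00 | Day 2 12:00 | Day 3 04:00 |
| 08:00 | Day 2 20:00 | Day 3 12:00 |
| 12:00 | Day 3 00:00 | Day 3 16:00 |
| 18:00 | Day 3 06:00 | Day 3 22:00 |
| 23:59 | Day 3 11:59 | Day 4 03:59 |

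- *t* + 36 ≥ 48 when *t* ≥ 12. For anyone randomised at noon or later, every Day 2 draw can precede the first unit.
- *t* + 52 > 72 when *t* > 20 (or *t* > 22 on the 50 h count). For late-evening randomisations, dosing can outlast the whole Day 2 +1 window.
- A prompt start does not exclude a mid-course draw. A course can span 2 + 12 + 2 = 16 h, so one begun at 16:00 on Day 1 can end at 08:00 on Day 2.
- The latest possible start is just before noon on Day 3. Day 4 labs therefore always follow the start of the first unit. In the extreme case a draw in the first four hours of Day 4 could still precede the end of the second.

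**2. Illustration of frequency.** Assumptions that are not in the documents: randomisation uniform over 08:00-20:00, draw at 06:00 on Day 2 (hour 30), delay to first unit uniform over 0 to *L* hours. The time from randomisation to draw, *X* = 30 − *t*, is uniform on 10 to 22 with mean 16. The share drawn before the first unit is E[max(*L* − *X*, 0)] / *L*.

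- *L* = 12: only *X* from 10 to 12 counts. The integral of (12 − *x*) over that range is 2, and 2/12/12 = 1.4%.
- *L* = 24: (24 − 16)/24 = 33%.
- *L* = 36: (36 − 16)/36 = 56%.

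If the draw is moved to 06:00 on Day 3 with *L* = 36, *X* is uniform on 34 to 46 and the share is 2/12/36 = 0.5%.

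**3. Sensitivity.** With randomisation and draw times both uniform over 24 h and a fixed delay, the share of Day 2 draws before the first unit is about 0% (2 h delay), 12% (12 h), 50% (24 h) and 88% (36 h). The result depends almost entirely on a delay distribution that the documents do not give.

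**4. Consequence.** If a fraction *p* of Day 2 samples is pre-infusion, carries no product effect, and is unrelated to outcome, the expected between-arm difference at Day 2 is multiplied by 1 − *p*. For *p* between 1% and 56%, that factor is 0.99 to 0.44. Mid-infusion samples would reduce it further by an unknown amount.

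**The case against.** The strongest reply is that the documents never call the Day 2 sample post-dose or say it is meant to catch acute transfusion effects. Acute safety is tied to the infusion elsewhere: section 6.1.2 takes vital signs before, during and after it, Table 1 has an adverse-event check at product administration and daily in hospital, and section 8.5 collects transfusion reactions, TRALI and TACO at any severity. Laboratory change is one item in a list of secondary safety endpoints, and Safety Analyses plans tests on event proportions, not on laboratory change. Same-day dosing is the stated ideal, and section 6.1.1 describes infusion over about 4 hours. The Table 5 window already permits a Day 3 draw. An Operations Manual and a separate SAP, neither available here, may also say more.

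Most of this stands, and it limits the importance of the point. It does not remove it: the window permits a later draw without asking for one, and the rule as written lets a pre-infusion value into a named endpoint.

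Three stronger readings are tempting but unsupported:

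- **Acute transfusion harm would be missed.** It would not, given the infusion-linked checks above and the Day 4 labs.
- **Nearly all Day 2 samples precede the end of dosing.** Under the section 2 assumptions this reaches 94% (*L* = 24) or 96% (*L* = 36), but only by giving every participant the full 12-hour gap.
- **The arms differ in timing because plasma takes longer to release than saline.** This is possible, but nothing in the documents shows it. Both arms share the same timing rules.

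**Conclusion.** The point holds as a gap in the sampling rule. Day 1 is randomisation, dosing can start up to 36 h and end about 50 to 52 h later, and neither the Day 2 sample nor a routine lab used in its place has to follow the infusion. The likely effect is dilution of the Day 1 to Day 2 laboratory change and of the early antibody measurement.

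That dosing can fall after the Day 2 draw follows from the text. How often it does cannot be derived from it. The range of about 1% to 56% before the first unit rests on assumed randomisation hours, a fixed 06:00 draw and assumed delays. A reader might infer that trial conclusions are at risk, but the primary and key secondary endpoints do not use these samples. The change is worth making because it is specific and cheap.

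**What to change.** 1. **Schedule.** In Table 1 notes 10 and 11 and in Table 5, keep the Day 2 +1 window. Specify that the Day 2 sample, or a routine lab used in its place, is drawn after the infusion has ended where the window allows, using Day 3 when needed. If dosing ends too late for that, take the latest sample in the window and flag it. An unconditional rule would leave some participants randomised late in the evening with no compliant sample.

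2. **Data and analysis.** Record the draw date and time. In the SAP, which General Approach says is still to be developed, classify each Day 2 sample as pre-, mid- or post-infusion against the infusion times already recorded under section 6.1.2. Do not count pre-infusion samples as post-treatment change in the safety analysis. Keep Day 1 as the single baseline. Leave participants who were never dosed on the calendar schedule. If sampling is already complete, the classification can still be applied wherever draw times exist.

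3. **Separate wording point.** Section 4.4 ends participation "on day 29 (+3 days) after administration of convalescent plasma", whereas the schedule counts from randomisation, and the phrase does not fit the saline arm. The two passages must be reconciled.

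**Cost.** Draw time must be captured, since no section says that it is. Some routine Day 2 labs will no longer count, and some draws will move to Day 3. Otherwise the change is a sentence in the schedule and one derived variable.
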